3.1.2 Overall Design and Control Methods

This will be a randomized, double-blind, placebo-controlled, parallel groups, multicenter trial assessing the efficacy and safety of the rFSH preparation FE 999049 in subjects aged 35-42 years undergoing controlled ovarian stimulation for IVF / ICSI following a GnRH antagonist protocol. The primary endpoint is the cumulative ongoing pregnancy rate after the fresh cycle and cryopreserved cycles initiated within 12 months from the start of controlled ovarian stimulation. Thereby, the trial is designed to capture the clinical efficacy of a single controlled ovarian stimulation cycle in a more complete manner by following outcomes from both the fresh and subsequent cryopreserved cycles. Secondary endpoints include pharmacodynamic parameters of FSH action as well as efficacy and safety parameters related to controlled ovarian stimulation from the fresh cycle and subsequent cryopreserved cycles.

Controlled Ovarian Stimulation and Fresh Cycle

Subjects will be screened within 90 days prior to randomization for compliance with the inclusion and exclusion criteria. On day 2-3 of the menstrual cycle, subjects will be randomized in a 10:1 ratio to FE 999049 or placebo, and controlled ovarian stimulation will be initiated. FE 999049 and placebo will be self-administered subcutaneously using a pre-filled injection pen.

Subjects assigned to treatment with FE 999049 will receive a starting dose of 15 µg daily that is fixed for the first four stimulation days. Based on ovarian response, the dose may be adjusted by 3 µg, with

Trial Code: 000002 Date: 25 Apr 2018 E-Study Protocol-22377; Ver. 1.0

> Supersedes: None Page 40 of 159

dose increases implemented not more frequently than once every 2 days and dose decreases implemented per investigator's judgement. The minimum daily dose is 6 μ g, and the maximum daily dose is 24 μ g. Subjects assigned to placebo will have the injection pen dialed to the same value (dose) as if administered FE 999049. Subjects can be treated with FE 999049 or placebo for a maximum of 20 days. Coasting, use of dopamine agonist or any other drug to prevent early OHSS with the exception of GnRH agonist for triggering of final follicular maturation, are not allowed.

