6.1.11 Ongoing Pregnancy

If a vital pregnancy has been documented, the subject must attend a visit 8-9 weeks (56-69 days) after transfer.

The following must take place:

- Ultrasound (transvaginal or abdominal) of uterus to assess any ongoing pregnancy
- Drug accountability of progesterone vaginal inserts
- Recording of use of any concomitant medication
- Recording of adverse events

If at least one intrauterine viable fetus is identified, this confirms an ongoing pregnancy.

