All screened subjects will be accounted for. Screened subjects who discontinue from the trial prior to randomization are regarded as screening failures. Screening failures and their primary reason for screening failure will be tabulated. Screening failures will not otherwise be accounted for.

Subject disposition with respect to analysis sets will be tabulated. This table will include the number of subjects in the intention-to-treat (ITT) analysis set, the modified intention-to-treat (mITT) analysis set, the per-protocol (PP) analysis set, the safety analysis set, as well as the number of subjects who provided a separate informed consent for optional exploratory analyses. The number of subjects in the ITT analysis set will be used as denominator when calculating percentages.

A separate table will summarize the subject disposition with respect to analysis sets by trial site. This table will include the number of subjects in the ITT analysis set, the mITT analysis set, the PP analysis set, and the safety analysis set. The number of subjects in the ITT analysis set will be used as denominator when calculating percentages.

Subject disposition with respect to the timing of action taken during the COVID-19 pandemic will be tabulated using the ITT analysis set. Subject disposition will be summarized by whether a subject had exited the trial before or after the COVID-19 pandemic trial hold went into place. Of the subjects that had not yet exited the trial, the subject status (i.e.; in a cryopreserved cycle or not in a cryopreserved cycle) will be summarized. For subjects within a cryopreserved cycle, the cryopreserved cycle number will be summarized. For subjects not within a cycle, the most recent cycle completed and the number that had an ongoing pregnancy will be summarized. Additionally, for subjects that had not yet exited the trial, the time since randomization will be summarized by the following categories: <3 months, 3 < 6 months, 6 < 9 months, ≥ 9 months.

Subject attendance at selected trial visits and adherence to selected trial procedures will be tabulated. A detailed listing of selected missing trial assessments will be created. Included will be an indicator of whether the corresponding visit took place, an indicator of whether the visit was expected to occur before, during, or after the COVID-19 pandemic trial hold period, and an indicator of whether the missingness was anticipated, unanticipated, or due to the COVID-19 pandemic.

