When applying the method of multiple imputation, three types of missingness are used: 1) missing the primary endpoint assessment from a recorded cryopreserved cycle because of the COVID-19 pandemic, 2) missing the primary endpoint assessment from a cryopreserved cycle that would have theoretically occurred had it not been for the COVID-19 pandemic, and 3) missing the primary endpoint assessment because of any other reason. The method of multiple imputation will only be applied to those endpoints that are missing because of the first two types of missingness. Missing endpoints because of the third type of missingness will continue to be imputed as 'negative'. If a

subject was still in the trial at the start of the COVID-19 pandemic trial hold and initiates an additional cryopreserved cycle after the end of the trial hold, but within 12 calendar months from their date of randomization, then this subject's endpoint will be considered non-missing and will not be imputed using multiple imputation.

Multiple imputation will be based on a risk-stratified hot deck imputation strategy. Subjects that are to receive imputation will be stratified by assigned treatment arm and the number of previous transfers within the study. The subjects not receiving imputation will form an imputation pool. The imputation pool will also be stratified by assigned treatment arm and the number of previous transfers within the study. If a stratum within the imputation pool contains fewer than 10 subjects, strata may be collapsed to increase the membership of a particular stratum. For each subject receiving imputation, the imputation pool will be further reduced to those subjects that have an endpoint assessment that occurred at or beyond the first date of missingness for the imputed subject's primary endpoint. Hot deck replacement commences from the reduced, stratified imputation pool 10 times, forming 10 analysis datasets from which combined estimates will be obtained using the method described by Rubin.⁵

For subjects with transfer but missing observations on the number of viable fetuses 8-9 weeks after transfer the number of viable fetuses will be imputed as zero irrespective of why data is not recorded. For subjects with transfer but missing information on the number of gestational sacs 5-6 weeks after transfer, the number of gestational sacs will be imputed as the number of viable fetuses 8-9 weeks after transfer.

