9.3.2 Sensitivity Analyses

The primary analysis will be repeated for the subjects in the PP analysis set as sensitivity analysis, as well as in the ITT analysis set if the ITT analysis set differs from the mITT analysis set. The outcomes of these analyses are considered supportive.

The primary analyses described above will be repeated restricted to subjects with oocytes retrieved and to subjects undergoing blastocyst transfer, as applicable.

Missing data for the primary endpoint is expected to be limited due to the trial design, but may occur if the subject is lost to follow-up before ongoing pregnancy is assessed. If one or more such subjects have a positive pregnancy test result (β hCG test, clinical pregnancy or vital pregnancy) prior to loss to follow-up, the impact of imputing the ongoing pregnancy will be investigated in a sensitivity analysis.

It is also possible that a subject without pregnancy assessments following a transfer has her birth/miscarriage/elective termination outcome available at a later time. The information may be evaluated to help determine the ongoing pregnancy status in the sensitivity analysis on a case-by-case basis.

In order to assess the impact, if any, of the COVID-19 pandemic on the primary endpoint, additional sensitivity analyses are planned which will assess both the timing of the COVID-19 pandemic trial hold and the imputation method applied to missing data that arises due to the pandemic. The primary endpoint analysis is based on cryopreserved cycles initiated within 12 calendar months from the date of randomization (subsequently referred to as 12 calendar months). However, for a subset of subjects, part of their 12 calendar months will have been lost due to the COVID-19 pandemic trial hold. These subjects will be allowed to initiate cryopreserved cycles within 12 months of active study days (subsequently referred to as 12 study months). Because the last randomization occurred on 17 September 2019 and the trial hold began subsequent to the issuing of Protocol Amendment 01 on 19 March 2020, the first COVID-19 pandemic sensitivity analysis will repeat the same methodology as the primary endpoint analysis (i.e.; same analysis set, same inference method, and same imputation method), but will instead use the cumulative ongoing pregnancy rate from cycles initiated within the

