9.4 Secondary Efficacy Endpoints

Secondary efficacy endpoints will be analyzed based on the mITT analysis set. As specified below, for selected endpoints, analyses will be repeated on the PP analysis set.

For secondary efficacy endpoints that are collected in the cryopreserved cycles, additional summaries will be tabulated by whether or not the cycle occurred before, concurrently during, or after the conclusion of the COVID-19 pandemic trial hold. It is anticipated that the number of cryopreserved cycles that are concurrent with or initiated after the COVID-19 pandemic trial hold will be small therefore only descriptive statistics, and not inferential statistics, will be applied to the three groupings.

Ferring Pharmaceuticals

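### The COVID-19 hot-deck imputation in SAP 9.2.2 ignores uncertainty in the donor success rate, so its combined variance is too small; the shortfall matters only if many recipients share few donors

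*SAP*

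**What the plan says.** SAP 9.2.2 limits multiple imputation to endpoints missing because of the pandemic. Recipients and donors are stratified by treatment arm and number of previous transfers. On small strata it says: "If a stratum within the imputation pool contains fewer than 10 subjects, strata may be collapsed". Next, "For each subject receiving imputation, the imputation pool will be further reduced to those subjects that have an endpoint assessment" at or after the recipient's first date of missingness. Then "Hot deck replacement commences from the reduced, stratified imputation pool 10 times, forming 10 analysis datasets from which combined estimates will be obtained" by Rubin's method. No resampling of donors and no draw of the success rate is described.

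SAP 9.3.2 uses this only in the third COVID-19 sensitivity analysis. The first counts cycles initiated in the first six calendar months and the second counts pregnancies within 12 study months. SAP 11.1.1 repeats all three for cumulative live birth, and SAP 9.2.1 calls additional analyses supportive. In the primary analysis these outcomes count as negative (SAP 9.2.2).

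**The concern.** Rubin's rules give a valid variance only if the imputations vary as much as our ignorance of the missing values warrants. Drawing 10 times from a fixed pool treats the observed donor rate as the true rate. Between-imputation variance then holds only the noise of the draws.

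The text does not prevent small pools. Collapsing below 10 is optional and is stated before the date reduction, so the pool actually drawn from has no minimum size.

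At stake is the credibility of one interval. This is the only COVID-19 analysis that uses multiple imputation for outcomes lost to the hold. If its interval is too narrow, the assessment of the pandemic's impact looks more precise than it is.

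**Working it through.** **1. The plan's own figure.** SAP 3.2 gives 500:50 subjects, 30% vs 3%, and power of at least 99%. The variance of the difference is 0.3×0.7/500 + 0.03×0.97/50 = 0.000420 + 0.000582 = 0.001002, so SE = 0.0317 and z = 0.27/0.0317 = 8.5. Power exceeds 99.9%, so the stated figure reproduces.

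**2. The omitted term.** Let donors have success rate p and v = p(1−p). The imputed arm total depends on the donor mean through (d+r)·p̂, whose variance is v(d+r)²/d = v(d + 2r + r²/d). Rubin's within part supplies about v(d+r) and the between part about vr. Together that is v(d+2r), so r²/d is missed. A pool of 10 serving 5 recipients loses almost nothing; the ratio of recipients to donors drives the size.

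**3. Size under assumed counts.** The documents give no r or d. Assumptions: all recipients are in the FE arm and share one pool (worst case), M = 10, and the overall FE rate is held at 30%. The upper donor rate is 32.3%, the rate per initiated cryopreserved cycle in Protocol 1.1; 10% is an assumed low value.

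- True variance = [V_other + (1+r/d)²·d·v + r·v(1−1/d)/M]/n² + 0.000582, where V_other is the variance of the count among the remaining FE subjects.
- Rubin variance = E[q(1−q)]/n + (1+1/M)·r·v(1−1/d)/n² + 0.98×0.000582, where q is the FE rate in one completed dataset.
- Even with complete data the Wald plug-in gives (0.000420×499/500 + 0.000582×49/50)/0.001002 = 0.988. The net ratio divides this out.

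Example, 40 recipients and 10 donors at 32.3% (v = 0.2187). The omitted term is 160×0.2187/500² = 0.000140. The true variance is (94.0 + 54.7 + 0.8)/500² + 0.000582 = 0.001180. The share is 11.9%.

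| r/d | omitted share, 32.3% | net ratio, 32.3% | omitted share, 10% | net ratio, 10% |
|---|---|---|---|---|
| 20/100 | 0.3% | 0.997 | 0.1% | 1.024 |
| 40/100 | 1.3% | 0.987 | 0.6% | 1.026 |
| 20/10 | 3.3% | 0.965 | 1.4% | 0.990 |
| 40/10 | 11.9% | 0.879 | 5.4% | 0.953 |
| 60/10 | 22.9% | 0.767 | 11.3% | 0.896 |

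Ratios above 1 arise because the pooled Wald variance is conservative when donors differ from the rest of the arm; there the omission is fully offset.

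**4. Simulation at 32.3%.** Raw Rubin/true ratios were about 0.87 (40/10) and 0.76 (60/10), and coverage of the 95% interval about 91% and 89%. Complete-data Wald coverage is 92.3%. A shared donor bootstrap raised coverage to 93–94% in both settings. At 40/100, coverage was 92.6% without and 92.8% with it.

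**5. Does the date reduction bite?** SAP 9.3.2: "last randomization occurred on 17 September 2019 and the trial hold began subsequent to the issuing of Protocol Amendment 01 on 19 March 2020". That is 184 days, so a first missing date at or after the hold lies at least 184 days after randomization. For treatment duration, Protocol 3.1.2 says: "Subjects can be treated with FE 999049 or placebo for a maximum of 20 days". Retrieval follows triggering by about 2 days, transfer is on day 5, and the ongoing-pregnancy visit ("must attend a visit 8-9 weeks (56-69 days" after transfer) falls by about day 20+2+5+69 = 96. If an endpoint assessment is an ultrasound visit, fresh-cycle visits cannot qualify a donor. If *date* also means calendar date, donors need a visit during or after the hold, and SAP 9.4 expects that "the number of cryopreserved cycles that are concurrent with or initiated after the COVID-19 pandemic trial hold will be small".

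**6. Superiority.** The SE would have to be 0.27/(1.96×0.0317) = 4.35 times larger for the lower limit to reach 0. The true SE at 60/10 is √0.001374 = 0.0371, or 1.17 times. In simulation the lower limit exceeded 0 in at least 99.99% of replicates.

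**The case against.** The strongest reply is that this hardly matters. The analysis is supportive, two other COVID-19 analyses need no imputation, and material bias requires 40–60 recipients on about 10 donors. Nothing in the documents points to that many recipients. They must still have been in the trial at the hold, anyone starting a further cycle afterwards within 12 calendar months is excluded, and the rest are split by arm and transfers. The 32.3% is also a poor match: it is a per-cycle rate, and the first of the two source trials enrolled women aged 18–40. Lower rates shrink the effect. All of this stands and limits the size, but the missing step remains missing.

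A reader might infer from the dates that only later cryopreserved-cycle visits can supply donors, so pools must be tiny. The documents do not establish this. SAP 9.3 also lets the endpoint be settled by exhausted blastocysts or by the status of cycles started within 12 months. SAP 9.2.2 treats women who choose not to return as having an observed one-year outcome. If that determination counts as an assessment, they are donors and pools may be much larger.

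A reader might also suppose that losses due to COVID-19 are not identified. They are: the listing in SAP section 4 carries "an indicator of whether the missingness was anticipated, unanticipated, or due to the COVID-19 pandemic".

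Finally, SAP 9.3.1 switches to Fisher's exact test below 5 placebo pregnancies. At 3% of 50 that has probability 98.3%, and Fisher's test has no variance for Rubin's rules to combine. This stands: the point concerns the combined estimate and its Wald interval, not the usual test.

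**Conclusion.** As written, the imputation is improper and its variance omits the donor-rate uncertainty. The size in this trial is unknown: negligible with plentiful donors, and material only if many recipients share few. The figures assume one shared pool, FE-arm recipients only, planning rates, and donor rates of 10–32%.

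A reader might conclude that the efficacy result is in doubt. It is not. The primary analysis does not use this imputation, and at the planning rates even the affected analysis keeps a lower limit well above 0. That is a statement about the planned rates, not about observed data. The point warrants a short revision of SAP 9.2.2.

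**What to change.** Revise SAP 9.2.2 as follows.

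- In each of the 10 datasets, resample donors once with replacement within arm and stratum (approximate Bayesian bootstrap). Share that resample across all recipients in the stratum, then apply the date reduction and draw. Sharing is essential: at 40/10 the raw ratio is 0.867 with no bootstrap, 0.867 with a separate one per recipient, and 0.969 with a shared one.
- Check the 10-donor threshold after the date reduction, collapsing across number of transfers within arm. If it still cannot be met, which is likely in a placebo arm of 50, use all eligible donors in the arm. If there are none, impute negative.
- Define *date* (calendar date or time since start of stimulation) and *endpoint assessment* (ultrasound visit only, or also the one-year determination).
- Report the Rubin-combined difference and its Wald interval as the result of this analysis, whichever branch of SAP 9.3.1 applies.

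Cost: one paragraph, a few lines of code and no new data. On a half-width of about 6.1 points, the interval widens by about 0.01 (20/100), 0.05 (40/100) or 0.1 point (20/10), 0.4 at 40/10, and up to about 1 point at 60/10. A small shortfall remains in very small pools: the net ratio with the shared bootstrap is 0.97–1.00.

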9.3 Primary Endpoint

The primary endpoint will be determined as soon as the subject has achieved an ongoing pregnancy, or when all cryopreserved blastocysts have been exhausted, or after assessment of ongoing pregnancy status in cryopreserved cycles initiated within 12 months from the start of controlled ovarian stimulation.

The superiority hypotheses to be tested for the primary endpoint are:

H₀: $\pi_{\text{FE 999049}} - \pi_{\text{Placebo}} \leq 0$ against the alternative H_A: $\pi_{\text{FE 999049}} - \pi_{\text{Placebo}} > 0$,

where $\pi_{FE 999049}$ and $\pi_{Placebo}$ denote the cumulative ongoing pregnancy rate after the fresh cycle and cryopreserved cycles in subjects aged 35-42 years treated with FE 999049 or placebo, respectively.

Ferring Pharmaceuticals

9.3.1 Primary Analysis

 H_0 will be tested against the alternative H_A by constructing a two-sided 95% confidence interval for the difference in the cumulative ongoing pregnancy rates between the two treatment groups using the traditional Wald interval. If the lower limit of the two-sided 95% confidence interval is greater than 0, the null hypothesis H_0 will be rejected. In the case that the number of pregnancies observed in the placebo group is small (<5), then the one-sided Fisher's exact test will be used.

The efficacy analysis will be based on the mITT analysis set, defined as all subjects who were randomized and received at least one dose of IMP (FE 999049 or placebo).

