3.2 Determination of Sample Size

The proposed sample size of 550 (FE 999049:placebo = 500:50) can adequately address both the efficacy and safety objectives of the trial:

- The cumulative ongoing pregnancy rate in the FE 999049-treated subjects aged 35-42 years is estimated to be approximately 30% according to results from clinical trials conducted in the U.S.¹ By comparison, the pregnancy rate in the placebo arm is expected not to exceed 3%, the monthly spontaneous pregnancy rate in infertile women.² Therefore, the proposed sample size of 550 (FE 999049:placebo=500:50) will provide at least 99% power for the primary efficacy comparison. Based on the estimated cumulative ongoing pregnancy rate, the cumulative live birth rate from the fresh and/or cryopreserved cycles is estimated to be approximately 27%, resulting in a power for the comparison of the cumulative live birth rate to be at least 99%.
- A key pharmacodynamic parameter in subjects aged 35-42 years is cycle cancellation due to poor follicular development, which may occur in approximately 5% of the population exposed to gonadotropins.
- The safety and tolerability of daily rFSH preparations as part of an ART treatment cycle have been well documented for the population studied in previous clinical trials.^{3,4} OHSS was reported to occur in 1.7% to 3.7% of the subjects, with moderate/severe OHSS occurring in 1.4% to 2.2% of the subjects. Other adverse events were pelvic pain, pelvic discomfort and headache, with those assessed to be related to trial treatments reported in 1.5% to 7.1% of the subjects.

Table 1 shows that the planned sample size of 500 subjects exposed to FE 999049 provides a high probability to detect a rare adverse event or safety signal occurring in 0.5% or more subjects.

Incidence rate of rare event	Chance of detecting at least 1 event
0.5%	91.8%
0.6%	95.1%
1%	99.3%

Table 1Probabilities to Detect at Least One Rare Event

Table 2 presents the margin width estimates of the 95% confidence intervals for a range of adverse event rates with the planned sample size.

Adverse event rate	Margin of error width estimate
5%	1.9%
10%	2.6%
15%	3.1%
20%	3.5%

Table 2Estimated Margin Widths of 95% Confidence Intervals

4 Subject Disposition

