9.2 Analysis and Presentation of Primary and Secondary Efficacy Endpoints

Summary tables and treatment comparisons for the primary endpoint will be presented for both the mITT and PP analysis sets. In case that the mITT and ITT analysis sets are not identical (i.e. at least one subject is randomized but not exposed) the summary tables and treatment comparisons will also be presented for the ITT analysis set. As applicable for the secondary endpoints, summary tables and treatment comparisons may be presented for the mITT and PP analysis sets.

All tabulations will be presented by treatment group. Continuous variables will be presented with number of subjects, mean, standard deviation, median, inter-quartile range, minimum, and maximum. Categorical variables will be presented with number and percentage of subjects within each specific category.

All statistical tests will be performed using a two-sided test at a 5% significance level. Treatment differences will (where appropriate) be presented with 95% confidence intervals and p-values corresponding to the statistical test of the hypothesis of 'equal effect' against the alternative of 'different effect'.

Visual displays will be produced as appropriate. All primary and secondary efficacy endpoints will be listed. Listings will only be produced for the mITT.

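### With 50 placebo subjects, the Wald branch of the primary decision rule lets one-sided type I error reach 4.65% to 4.87% instead of the implied 2.5%, and the level of the Fisher branch is not stated

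*SAP*

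**What the plan says.** SAP 9.3.1 compares the two cumulative ongoing pregnancy rates through the "traditional Wald interval" for their difference. The null is rejected "If the lower limit of the two-sided 95% confidence interval is greater than 0". The exception begins "In the case that the number of pregnancies observed in the placebo group is small (<5"): the one-sided Fisher's exact test then takes over. Protocol 9.7.2 has the same rule. Neither place gives the level at which the one-sided Fisher p-value is judged.

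Three other statements bear on the level. SAP 9.2 says "All statistical tests will be performed using a two-sided test at a 5% significance level". SAP 9.2.1 requires significance of the primary endpoint at 0.05 before live birth is tested, and claims strong control of the overall type I error at 0.05. SAP 11.1.1 applies a similar method to cumulative live birth.

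For the design, SAP 3.2 has "The proposed sample size of 550 (FE 999049:placebo = 500:50"), an FE 999049 rate that "is estimated to be approximately 30" percent, and says that "the pregnancy rate in the placebo arm is expected not to exceed 3" percent. It states that this "will provide at least 99% power for the primary efficacy comparison".

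**The concern.** Rejecting when the lower limit of a two-sided 95% interval exceeds zero is a one-sided test at a nominal 2.5%. The unpooled Wald interval takes its variance from the observed rates. With 10:1 allocation most of that variance comes from the 50 placebo subjects. When placebo does badly by chance, the difference grows and the standard error shrinks together, so the limit clears zero too easily.

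Fisher's test is conservative, so two tests of very different strictness meet between 4 and 5 placebo pregnancies. Depending on the Fisher level, one extra placebo pregnancy could move the result from not rejected to rejected.

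This rule decides the primary claim and opens the formal live-birth test. SAP 9.3.2 also repeats it in the per-protocol set, and in subjects with oocytes retrieved or with a transfer, where the placebo denominator cannot exceed 50.

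**Working it through.** **Inputs.** 500 and 50 subjects, 30% and 3% (SAP 3.2); Wald lower 95% limit above zero if placebo has 5 or more pregnancies, otherwise one-sided Fisher (SAP 9.3.1). The Fisher level is unstated, so 0.025 and 0.05 are both computed. It is assumed that all randomized subjects are dosed, so the mITT set is 500:50. Missing outcomes count as not pregnant (SAP 9.2.2), so no subjects are lost.

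**Step 1: the plan's power.** Normal approximation with pooled null variance:
- p̄ = (500×0.30 + 50×0.03)/550 = 0.2755
- SE₀ = √[0.2755×0.7245×(1/500 + 1/50)] = 0.0663
- SE₁ = √[0.30×0.70/500 + 0.03×0.97/50] = 0.0317
- power = Φ[(0.27 − 1.96×0.0663)/0.0317] = Φ(4.43) = 99.9995%

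Exact power of the combined rule is 99.9985% at 30% vs 3% and 99.99% at 27% vs 3%. The stated 99% is reproduced.

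**Step 2: exact type I error.** Let x₁ and x₀ be the FE 999049 and placebo counts. For a common rate π, sum Bin(x₁; 500, π)×Bin(x₀; 50, π) over all rejecting tables among the 501×51 possible.

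| Common rate | Rule, Fisher 0.025 | Rule, Fisher 0.05 | Wald alone | Fisher 0.025 alone | Pooled score |
|---|---|---|---|---|---|
| 3% | 0.0% | 0.0% | 21.8% | 0.0% | 0.0% |
| 5% | 0.06% | 1.0% | 9.0% | 0.06% | 0.15% |
| 10% | 1.1% | 2.6% | 7.1% | 1.1% | 1.4% |
| 17% | 2.3% | 3.8% | 5.5% | 1.4% | 1.8% |
| 20% | 4.4% | 4.9% | 5.0% | 1.5% | 1.9% |
| 25% | 4.4% | 4.4% | 4.4% | 1.6% | 2.1% |
| 30% | 4.0% | 4.0% | 4.0% | 1.7% | 2.2% |

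With Fisher at 0.025 the maximum is 4.65%, at a rate of 0.218; the error exceeds 2.5% from about 17% to 58%. With Fisher at 0.05 the maximum is 4.87%, at 0.20; it exceeds 2.5% from about 9% to 58%. The first part of that second range (2.6% at 10%) comes from running Fisher at 0.05, not from Wald.

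**Step 3: source of the peak.** At 0.218, 3.87 of the 4.65 points come from tables with 5 or more placebo pregnancies (Wald) and 0.78 from the rest. Wald used for every table would reach about 46.5%, at a rate near 1%.

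**Step 4: the 4/5 boundary.** Smallest number of FE 999049 pregnancies that rejects:

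| Placebo pregnancies | Fisher 0.025 | Fisher 0.05 | Wald | Pooled score |
|---|---|---|---|---|
| 4 | 100 | 90 | 81 | 97 |
| 5 | 113 | 102 | 95 | 109 |

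The rule reads the Fisher column at 4 and the Wald column at 5. With Fisher at 0.025 the requirement falls from 100 to 95. For example, 96/500 vs 4/50 has Fisher p = 0.031 and fails. At 96/500 vs 5/50 the limit is 0.092 − 1.96×√(0.192×0.808/500 + 0.10×0.90/50) = 0.092 − 0.090 = +0.002, which succeeds although the Fisher p has risen to 0.073. With Fisher at 0.05 the requirement rises from 90 to 95, so there is no reversal.

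**Step 5: why Wald is lenient.** At 95/500 vs 5/50 the unpooled variance is 0.00031 + 0.00180 = 0.00211, of which placebo contributes 85%, and z = 0.09/0.0459 = 1.96. The pooled null variance is (100/550)×(450/550)×0.022 = 0.00327, giving z = 0.09/0.0572 = 1.57 and one-sided p = 0.058.

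**Step 6: how often Wald is used.** The chance of 5 or more placebo pregnancies is 1.7% at a 3% placebo rate, 10% at 5% and 57% at 10%.

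**The case against.** Much of the opposing case stands.

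- A reader might infer that the data-driven switch causes the inflation. It does not. Fisher removes the very large Wald error at low rates, and near 22% the combined rule (4.65%) is marginally below Wald alone (4.73%). Deleting the switch while keeping Wald would make the plan much worse.
- A reader might treat the reversal at 4 versus 5 as a fixed property of the plan. It requires Fisher at one-sided 0.025. The documents state no level, and since SAP 9.1.1 and 9.2.1 speak of a 0.05 alpha level, 0.05 is a possible reading.
- A reader might infer that the SAP's stated error control fails. Both maxima are below the 0.05 in SAP 9.2.1. The 2.5% benchmark is inferred from the two-sided 95% limit and two-sided 5% testing, although that inference is the natural one.
- A reader might infer that the trial's expected conclusion is at risk. At 30% vs 3% the rule's power differs from that of Fisher at 0.025 by 0.012 percentage points and from the score test by 0.007.

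What does not stand is the view that the planned rates make the rule's error rate irrelevant. The 3% is a planning assumption, and protocol 3.5.1 itself says that the placebo response in this population is not well characterized. An error guarantee should not depend on that assumption.

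**Conclusion.** The concern holds in limited form. The primary decision rule does not hold the one-sided 2.5% implied by its two-sided 95% limit. Its maximum is 4.65% or 4.87%, depending on an unstated Fisher level, and the peak arises mainly from the unpooled Wald limit with 50 placebo subjects. The non-monotone boundary is a separate defect, present only if Fisher is run at 0.025. The missing level is a gap in its own right.

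These figures rest on 500:50 analysed and on binomial outcomes with a common rate under the null. The excess needs common rates above about 17% (Fisher at 0.025) or about 9% (Fisher at 0.05), far above plan. The change should be made because it is cheap and concerns the primary claim; the conclusion at the planned rates is very unlikely to depend on it.

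**What to change.** In SAP 9.3.1 and protocol 9.7.2, replace both branches, Wald included, with one test for every placebo count, and state its level. Either option works:

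- a score test with its matching interval (for example Miettinen-Nurminen) at two-sided 5%. The maximum one-sided error of the pooled score test is 2.5% for common rates up to 0.5; it can exceed this at extreme rates near 1.
- Fisher's exact test at one-sided 0.025. Maximum error is 1.8%.

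Both are monotone at the 4/5 boundary. Use the same rule for cumulative live birth in SAP 11.1.1. The switch must not be deleted while Wald is kept.

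The change is wording only, to be made before the blind is broken. Planned power is 99.99% at 30% vs 3% for either test, and 99.9% at 27% vs 3%. The real cost is power if placebo is far above plan: at 30% vs 10%, 92% (score) or 91% (Fisher) against 96% for the current rule; at 25% vs 10%, 73% or 69% against 84%.
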